Table 1: Demographic Overview of Study Sites

Company name	Location	Type of Industry	Number of Employees	Employee Age-range	Percent Women
Chennai Petroleum Corporation Ltd	Chennai	Oil Refinery	1,500	30-55	1-2%
L&T Infotech	Chennai	Technology and Business Services	3-5,000	20-50	30-35%
Cognizant Technology Solutions	Chennai	Technology and Business Services	50,000	25-55	30-40%
Rourkela Steel Plant	Rourkela	Mining and Steel Manufacturing	18,000	19-65	26%
TATA Consultancy Services	Chennai	Technology and Business Services	50,000	25-55	30-40%
Bokaro Steel Plant	Bokaro	Mining and Steel Manufacturing	19,000	19-65	31%
Bhilai Steel Plant	Bhilai	Mining and Steel Manufacturing	30,000	19-65	27%
TATA Steel	Jamshedpur	Mining and Steel Manufacturing	36,418	19-65	29%

Study Sample: Inclusion criteria are: aged ≥ 18 years; overweight or obese using World Health Organization defined South-Asian cut-points: BMI ≥ 23 kg/m² and/or waist circumference ≥ 90 cm for men and ≥ 80 cm for women;⁷⁵ have prediabetes (HbA_{1c} of 5.7-6.4%) or diabetes (HbA_{1c} $\geq 6.5\%$); not currently taking any diabetes medications; not pregnant or breastfeeding; and without history of heart disease, current serious illness, or conditions which would impede participation in an unsupervised physical activity and diet change program.

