Eligible individuals will be identified using a two-phased screening program at each worksite. All interested workers at the study site will be allowed to attend the Phase 1 screening visit and will be provided with a health report describing the results of the screening visit to share with their doctor. **Phase 1 Screening** will entail a short questionnaire with questions on demographics and general health behaviors and the Indian Diabetes Risk Score (IDRS) questionnaire, anthropometric measurements (height, weight, and waist circumference), and random capillary glucose (RCG) measurement. IDRS is simple to administer, includes only four questions (on age, waist circumference, physical activity, and family history of diabetes), is a reliable instrument for identifying individuals with diabetes and prediabetes, and can be easily used in the field and during program dissemination.^{76,77} Individuals with a RCG ≥ 110 mg/dl or IDRS > 30 will be invited for Phase 2 Screening. **Phase 2 Screening** will include a fasting blood draw to measure HbA_{1c}, glucose, and plasma lipids, blood pressure measurement, anthropometric measurements (height, weight, waist circumference), and a study questionnaire. The screening program will need to be low-cost and easy to incorporate into a workplace setting, while still successfully identifying patients with prediabetes and diabetes. HbA_{1c} testing is easy, can be done on a non-fasting individual, is relatively inexpensive, and is recommended as a diagnostic tool for diabetes and prediabetes by expert groups including the American Diabetes Association.^{41,78} Eligible and consented individuals will be enrolled in the lifestyle

Figure 1: Worksite intervention protocol

[figure not shown]
* RCG = random capillary glucose; IDRS = Indian Diabetes Risk Score; HbA_{1c} = glycosylated hemoglobin; BMI = body mass index

education program, and all individuals attending screening will receive a report of their results. Any individual presenting with results indicative of a health condition, including diabetes, will be referred to their primary care or company physician for clinical follow-up.

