Preliminary data: D-CLIP [clinicaltrials.gov #NCT01283308, Emory University and Madras Diabetes Research Foundation (MDRF) investigators] is an on-going, translational, diabetes prevention study comparing standard lifestyle advice to a step-wise, culturally tailored program (group lifestyle classes plus metformin for participants not responding to lifestyle change alone) among 602 people with prediabetes in India.²⁵ D-CLIP was developed based on the DPP Curriculum.^{79,80} Early unpublished D-CLIP results are promising. The participation rate for intervention classes was high (83%), and loss to follow-up was low (9%). At eighteen months, lifestyle participants had significantly greater reductions in weight (-1.7 vs. -0.8 kg), BMI (-0.6 vs. -0.3 kg/m²), and waist circumference (-2.7 vs. -2.0 cm) than controls. Additionally, intervention participants showed greater improvements in systolic blood pressure, triglycerides, and HbA_{1c}; 21% of controls achieved improvement in two or more of these risk factors while 33% of intervention group did so. Similar to previous studies showing that weight, BMI, and waist circumference reductions significantly predicted diabetes risk reduction in lifestyle interventions,⁸¹ preliminary D-CLIP analyses show a 51% relative risk reduction in diabetes incidence in intervention participants compared to controls. The effects of the D-CLIP intervention were consistent across sex, age, income, education, and baseline BMI and glucose intolerance.⁸²

Recommendations for improving the Indian diet to better prevent diabetes and reduce cardiometabolic risk factors will be developed based on the work assessing the value of improving food quality of the Global Nutrition and Epidemiologic Transition (GNET) initiative at Harvard University and MDRF. For example, a small crossover trial of substituting brown rice for white rice for five days, found that brown rice lowered glucose levels by 19.8% and fasting insulin by 57%.⁴⁰ GNET studies in other populations further support benefits of improving carbohydrate quality.³⁸ Moreover, studies of acceptability of brown rice in India indicate that well-informed, sensory trained panelists readily accepted brown rice,³² but translating this intervention to the public

Figure 2: Components of the Lifestyle Intervention at the Individual and Worksite Environment Levels

will require additional education and training.²⁷

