Quantitative data collection (Table 4) will occur at study-testing visits at baseline and every twelve months after lifestyle classes begin. Whenever possible, validated study instruments will be used. The primary outcome assessing program effectiveness (Aim 2) will be a composite of achieving two or more cardiometabolic risk goals; participants will be scored on the number of risk factors they improve on (0-3) with success delineated by a HbA_{1c} decrease $\geq 0.5\%$; a systolic blood pressure decrease ≥ 5 mm Hg; and a decrease in plasma triglycerides ≥ 10 mg/dl. This outcome was selected for three reasons: other risk scores for CVD (e.g., the Framingham Risk Score) do not perform as well in South Asian populations;⁹³ these risk factors are commonly measured by clinicians, so the results are clinically appropriate; and the composite outcome allows for individual variation in risk factor profiles and the ability of individuals to reduce different factors (e.g., an individual with a baseline HbA_{1c} of 5.8% is unlikely to reduce this risk factor by 0.5%, but may succeed in reducing triglycerides or blood pressure).

Table 4: Quantitative Data Collection Tools

Variable of interest (test)	Outcome of test	Timing			
		S	B	A	FU
Demographics and Lifestyle Behaviors					
Demographics (SQ)	Describe study population	X	X		
History of smoking (SQ)	Smoking status and cessation rates		X	X	X
Global Physical Activity Questionnaire (GPAQ) ⁹⁴	Baseline and changes in physical activity		X	X	X
Dietary intake (food frequency questionnaire)	Study specific food frequency questionnaire on dietary intake of foods targeted in the intervention		X	X	X
Dietary behaviors (SQ)	Prevalence of diet-related behaviors (e.g., reading nutrition		X	X	X

Variable of interest (test)	Outcome of test	Timing			
		S	B	A	FU
Weight loss history (SQ)	labels, eating at restaurants, measuring portions, etc.) Weight loss history including number and success of past attempts, methods used, etc.		X		
Quality of life (EQ-5D)	Baseline and changes in quality of life		X	X	X
Self-reported health (SF-12 and SQ)	Health status, recent health events and medication use (type and dosage of all prescription and over the counter medications and herbal remedies)		X	X	X
Worker satisfaction (SQ)	Questions assessing worker satisfaction with worksite, number of days missed work, self-described levels of productivity		X	X	X
Health-related outcomes					

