Aim 2: Statistical analysis of intervention impact: A generalizing estimating equations (GEE) framework for clustered data⁹⁷ will be used to assess the statistical significance of any observed intervention effect on the endpoints. For the primary endpoint, the dependent variable will be the indicator for whether the study participant is at two or more cardiometabolic risk factor reduction goals at the end of the 3 year follow-up period, minus the expected probability of this endpoint in the absence of an intervention, to be taken as 21% as observed in the D-CLIP²⁵ control group. An exchangeable working correlation matrix will be used to incorporate the clustering within the 8 work-sites, with a log link and binomial variance specified. The exponentiated point and interval estimates from the intercept of this model will quantify the intervention effect, and the p-value associated with the model's intercept will provide a measure of the statistical significance of the findings. A similar GEE approach will be used to estimate and test the significance of intervention effects on secondary endpoints. For continuous markers, such as systolic blood pressure and HbA_{1c}, the post- to pre- within-participant difference will serve as the dependent variable in a GEE model as above, with the identity link function and the distribution specified as normal. The change scores will be evaluated for outliers, and analysis will be repeated with and without extreme outliers. For the cumulative incidence of diabetes at end of follow-up, participants will be coded as one if they satisfy the diabetes definition at end of follow-up and 0 otherwise. A Cox proportional hazards regression model for the diabetes incidence rate will also be considered, and if dropout or loss to follow-up are non-negligible, causal methods for adjusting for dependent censoring will be applied.¹⁰² A similar approach will be used to assess regression to normoglycemia. We will consider worksite-level covariates in multi-level models to examine how these aspects might affect findings. Additional secondary endpoints will be considered (e.g., changes in being at 1, 2 and 3 CVD/T2DM risk factor goals). Although the study is not powered to detect it unless quite large and although no effect modification is expected, we will assess the presence of effect modification by calculating intervention effect estimates stratified by potential modifiers, such as gender, age, marital status, socio-economic status, and assess the statistical significance of any effect modification observed by calculating a cross-product term between the potential modifier and the intervention, using a robust score test to assess the significance of

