Sample Size Selection: This worksite-clustered before-after design of 8 worksites with at least 250 eligible and enrolled participants per site and no more than 20% loss to follow-up (LTF) after 3 years will have 93% or more power to detect an estimated difference between the percent of participants at 2 or more CHD risk factor goals after 3 years of follow-up, the primary effectiveness endpoint of this trial, of 33% or greater, compared to the comparable D-CLIP²⁵ percentage of 21%. The 20% 3-year LTF rate is likely conservative, as only 9% of D-CLIP participants have been lost to follow-up after a mean of 30 months. Similarly, the D-CLIP comparative percentage of 21% is likely conservative, because the D-CLIP control group also experienced a minimal intervention that included meeting with a physician and a dietician, attending two classes (a lecture on diabetes

prevention through weight loss and diet change, and an exercise class), and receiving handouts reinforcing prevention of T2DM. Thus, compared to a community control receiving none of these services, the D-CLIP group would be expected to have a higher percentage at or exceeding two goals, compared to the community standard. In addition, power in this study is excellent for numerous secondary effectiveness endpoints of considerable interest, including 90% power or more to detect a decrease of 2mmHg or greater in systolic blood pressure ($p=0.10$, IIS), 95% power or more to detect a decrease in HbA_{1c} of 0.14% or greater ($p=0.10$, IIS), and nearly 100% power to detect a reduction in diabetes incidence of 30% or greater among the 2/3 of the study participants with prediabetes at baseline screening, compared to the baseline rate of 0.07/year,¹²⁴ otherwise under the same assumptions as the primary endpoint calculation.

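### The primary endpoint counts risk-factor falls regardless of drugs started after baseline and reads them as the lifestyle effect; a drug-adjusted analysis should be pre-specified beside it

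*Combined protocol and SAP*

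**What the plan says.** The endpoint is defined under Data Collection (quantitative): "participants will be scored on the number of risk factors they improve on (0-3"), with goals of an HbA1c fall of at least 0.5%, a systolic fall of at least 5 mm Hg and a triglyceride fall of at least 10 mg/dl. Under Data Analysis, Aim 2, "the dependent variable will be the indicator for whether the study participant is at two or more cardiometabolic risk factor reduction goals" after three years. From this is subtracted an expected probability without intervention, "to be taken as 21% as observed in the D-CLIP" control group. The exponentiated model intercept is then read as the intervention effect. Neither place mentions drug use.

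Four other places bear on this:

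- **Study Sample, inclusion criteria.** Participants must be "not currently taking any diabetes medications". This is an entry condition only. Blood-pressure and lipid drugs are not restricted. HbA1c of 6.5% or more is eligible, and Sample Size Selection puts prediabetes at two thirds of the sample, so about one third have untreated diabetes.
- **Study Sample, screening.** "Any individual presenting with results indicative of a health condition, including diabetes, will be referred to their primary care or company physician".
- **Table 4.** Data collected at baseline, annually and at the end include "recent health events and medication use (type and dosage of all prescription and over the counter medications and herbal remedies"). A cost questionnaire covers medicines for diabetes, blood pressure and lipids. The stated uses are Aim 3 (health status, utilisation and economic analysis).
- **Preliminary data.** D-CLIP compared standard advice with a stepped programme ("group lifestyle classes plus metformin for participants not responding to lifestyle change alone) among 602 people with prediabetes in India").

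The marginal structural models at the end of the Aim 2 text are for non-adherence and loss to follow-up.

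**The concern.** Each of the three goals is a direct target of common drugs. The trial selects people with untreated diabetes, tells them so and sends them to a physician. Someone who attends no class but starts treatment after that referral, and so reaches a second goal, is a programme success at three years.

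In a randomised comparison, much of this would cancel between arms. Here there is no concurrent arm. The benchmark is a constant from people with prediabetes, so it cannot contain treatment starts among people who already have diabetes. Aim 2 is about the effectiveness of the programme, which the protocol describes as classes plus worksite changes. A rate above 21% would mix that effect with the effect of screening, referral and prescribing. Regression to normoglycemia has the same gap, because no rule covers normal values on a drug.

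**Working it through.** **1. What the plan fixes and what it leaves open.** From Sample Size Selection: 8 sites × 250 = 2,000 enrolled; 20% loss leaves 1,600 (200 per site); 33% against 21%; power at least 93%. Significance is at 0.05 (Data Analysis). No ICC is given for the primary endpoint, and the documents give no rate of drug starts, no success rate on drugs and no drug use among D-CLIP controls.

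**2. The plan's own power.** For a one-sample test against p0 = 0.21, with n = 1600/[1 + 199 × ICC]:

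power = Φ{[(p1 − p0) − 1.96·√(p0(1 − p0)/n)] / √(p1(1 − p1)/n)}

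With p1 = 0.33 this gives 91.7% at ICC 0.05, exactly 93% at ICC 0.047 and 70.4% at ICC 0.10. The stated figure cannot be reproduced without assuming an ICC. The point here does not depend on it, but the formula is reused in step 5.

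**3. Illustration in the diabetes third.** All of the following are assumptions: no lifestyle effect; independent normal changes with mean zero and SD 14 mm Hg (systolic), 60 mg/dl (triglycerides) and 1.0 (HbA1c, in % units); a glucose drug lowers HbA1c by 1.0 on average. The chance of meeting each goal is:

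- systolic: Φ(−5/14) = 0.360
- triglycerides: Φ(−10/60) = 0.434
- HbA1c without a drug: Φ(−0.5) = 0.309; with a drug: Φ(+0.5) = 0.691

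With h the HbA1c probability, the chance of two or more goals is 0.360 × 0.434 + h × (0.360 + 0.434 − 2 × 0.360 × 0.434) = 0.156 + 0.482h. This is 30.5% without a drug and 48.9% with one, a gain of 18.4 points per starter.

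**4. Spread over the whole sample.** The overall shift is (1/3) × share starting × 18.4 points.

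| Share of diabetes third starting | Rate in that third | Shift overall |
|---|---|---|
| 0% | 30.5% | 0 |
| 25% | 35.1% | 1.5 points |
| 50% | 39.7% | 3.1 points |
| 75% | 44.3% | 4.6 points |
| 100% | 48.9% | 6.1 points |

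Blood-pressure and lipid drugs, and any starts in the prediabetes group, are not in this table.

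**5. Chance of a significant result with no lifestyle effect.** Take 21% as the true drug-free rate and add 4.6 points (p1 = 0.256):

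- ICC 0.01: n = 535.1; (0.046 − 0.0345)/0.0189 = 0.61; about 73%
- ICC 0.05: n = 146.1; (0.046 − 0.0660)/0.0361 = −0.56; about 29%
- ICC 0.10: n = 76.6; (0.046 − 0.0912)/0.0499 = −0.91; about 18%

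The nominal upper-tail rate is 2.5%.

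**6. Power of a stricter endpoint.** If 3, 5 or 7 of the planned 33 points were drug-assisted and not counted, the rates would be 30, 28 and 26%. Power against 21% at ICC 0.05 falls from 92% to 74%, 54% or 33%.

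**The case against.** The strongest reply is that counting outcomes regardless of drugs is a legitimate choice for an implementation study; the Aim 3 costing even lists screening as a component of the intervention. That stands as far as it goes, and it is why the endpoint should be kept. But the plan does not state this choice, the benchmark does not match it, and the intercept is called the intervention effect.

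Second, Aim 3 already models medication use and health status over time, by adherence and by baseline diabetes versus prediabetes, and Aim 1 measures weight, diet and activity. These would help a reader interpret the result. They do not link a participant's drug start to that participant's primary outcome.

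Third, the direction is not certain. The Significance section reports that lifestyle participants in a cited trial needed less blood-pressure and lipid medication. A participant whose drug is reduced may miss a goal, which counts against the programme. Drug starts among D-CLIP controls may also lie inside the 21%; the documents do not say. Both points stand.

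Three stronger readings are tempting, and the documents do not support them:

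- **That drugs could explain the whole planned difference** ("of 33% or greater, compared to the comparable D-CLIP" figure of 21%). This needs 12 points × 1,600 = 192 completers, or 36% of the diabetes third, to reach a second goal only through a drug. The illustration yields at most 18 points in that third and 6.1 overall.
- **That about 46% of the sample is exposed by year three**, from 1/3 + 2/3 × (1 − e^(−0.07 × 3)). Participants who progress from prediabetes would still have to fall 0.5% below their own prediabetes baseline. The protocol itself calls this unlikely for someone starting at 5.8%.
- **That success should require both versions of the endpoint to exceed the benchmark.** Against a common 21%, the stricter version simply becomes the primary endpoint, with the power loss in step 6.

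**Conclusion.** The omission is clear from the text: drug starts and increases after baseline are counted towards the primary endpoint, the design has nothing that cancels them, and the planned causal models do not address them. Followed as written, the plan can credit prescribing to the lifestyle programme.

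The size is not derivable. The 1.5 to 4.6 points, and the 73%, 29% and 18% chances of a significant result, rest on the assumed SDs, drug effect, start rates and ICCs, and on independence of the three changes. Only the drug-related shift should be taken from the illustration. Its 30.5% drug-free rate in the diabetes third, against 21%, reflects the assumed variability and the comparability of the benchmark, which is a separate matter. Confidence is high in the gap and low in its magnitude. This should be fixed and is cheap to fix; it does not invalidate the endpoint.

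**What to change.** In Data Analysis, Aim 2:

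1. Keep the primary endpoint and state that it counts goals met regardless of drug use.
2. Pre-specify beside it an analysis from the Table 4 medication data in which a goal does not count if a drug for that factor was started or increased since baseline.
3. Add a companion analysis that takes account of drugs reduced or stopped.
4. Apply the same rule to regression to normoglycemia.
5. Report all of these by baseline diabetes status, with the numbers of drug starts, increases and reductions for each factor.
6. Attribute the effect to the lifestyle programme only to the extent that it persists in the drug-adjusted analysis. Note that the 21% is not drug-adjusted unless D-CLIP drug data can be obtained; the documents do not show that they are available.

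The cost is wording and programming, since the participant data are already collected. The downside is real: the drug-adjusted rate will be lower and less powerful, it discards some falls achieved by lifestyle, and it is compared with an unadjusted benchmark. It should therefore be supportive and not a second success criterion. No change to referral or care is involved.

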When appropriate, all data analysis will be conducted for the entire study and individually by site. Qualitative data will be comprised of the translated, verbatim transcripts of the in-depth interviews and FGD. Textual data will be managed using the MAXqda10 (VERBI Software, 1989-2012). A codebook for each set of qualitative data will be created, tested for inter-coder reliability, and used to code the transcripts. When appropriate, qualitative data will be used to modify and improve intervention components and guide selection of adaptable components at each site. De-identified quantitative data will be entered into Microsoft Access databases. Range checks, disallowing invalid values, and adaptive double entry, along with regular data audits will ensure the accuracy of the electronic data. Data analysis will be conducted using SAS primarily. Descriptive analysis will be performed for all variables and outliers will be investigated for data errors. A probability of <0.05 will be considered statistically significant for all tests.

Aim 1: Success of program implementation will be assessed as follows:

- a) Program Adoption: Program adoption will be measured by quantifying participation in the program and success in reaching the goals of the lifestyle education program (weight loss, increased physical activity and diet improvements). Participation will be measured by calculating the percentages of total employees agreeing to screening, agreeing to participate in the program, and enrolling in lifestyle classes. Attendance records for study classes and other activities and numbers of diet/activity tracking booklets turned in for review by the health educator will be reviewed to determine percent attendance at each class and at classes overall. Physical activity [in Metabolic Equivalent of Task (METS)/day] will be quantified using the Global Physical Activity Questionnaire (GPAQ).⁹⁴ Diet changes will be quantified through a study-specific food frequency questionnaire, which will include food items that participants are encouraged to eat more or less often, as well as questions on diet-related behaviors (e.g., reading food labels, measuring portion sizes). A healthy diet score will be calculated from the food frequency questionnaire and other diet related questions.^{95,96} Changes in weight, BMI, waist circumference, physical activity, and diet score over time will

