
this term.⁹⁷ To assess the causal effect of the intervention adjusted for bias due to non-adherence and loss to follow-up, marginal structural models will be fit, embedded around the analysis approaches outlined above.¹⁰³ The study statistician, [name], has substantial experience fitting these causal models to adjust for time-dependent confounding and dependent censoring, e.g.¹⁰⁴⁻¹⁰⁷.

Aim 3: Impact of the intervention on workers and worksite: Qualitative data from interviews with employees on job satisfaction and views of the company and worksite will be described using the thematic analysis methods described in Aim 1. The analyses below are aimed at helping stakeholders that might consider adopting this intervention program to be fully informed of the upfront (fixed) and recurring (variable) costs to deliver the intervention and the potential return on investment (ROI). We will use an employer/societal perspective and will report cumulative and per-site estimates. Analyses for this aim will include:

- a) **Estimating total costs to deliver the intervention:** we will estimate average fixed and variable costs of delivering the lifestyle change program at worksites in India. Specifically, we will collect cost data from each worksite regarding components of the intervention: 1. Screening for high-risk individuals; 2. Delivering the individual lifestyle education program (per employee enrolled), which include labor costs for lifestyle coaches and classes and education materials; and 3. Changing the work environment (per campus and per 1,000 employees), which include costs for subsidizing purchase and preparation of healthy foods, as well as any capital costs (e.g., gym facilities, walking paths).
- b) **Staff productivity (absenteeism; presenteeism) and indirect costs:** Absenteeism will be calculated from worksite attendance records. To assess presenteeism, we will administer a questionnaire that captures performance of employees (specific markers of productivity for each worksite and employee function). We will calculate indirect costs (monetary value of lost productivity) using the human capital approach (multiplying combined days lost to absenteeism plus presenteeism by salary of different occupational roles). Changes in these measures over the course of the program will be modeled for each study site and for all study sites using mixed methods models.

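### The primary GEE states no analysis set and no rule for missing 3-year outcomes, and the only loss adjustment that reaches it is combined with non-adherence

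*Combined protocol and SAP*

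**What the plan says.** All references are to the combined protocol and SAP.

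- **Primary analysis (Data Analysis, Aim 2).** The dependent variable is "the indicator for whether the study participant is at two or more cardiometabolic risk factor reduction goals at the end of the 3 year follow-up", less a fixed 21% taken from the D-CLIP control group. The GEE intercept and its p-value are the stated result. No analysis set, imputation method or missing-value rule is given.
- **Outcome definition (Data Collection).** Success means meeting at least two of three thresholds for decrease, in HbA1c, systolic blood pressure and triglycerides. It cannot be scored from a missing 3-year visit.
- **Expected loss (Sample Size Selection).** The design has "8 worksites with at least 250 eligible and enrolled participants per site", with an allowance of "no more than 20% loss to follow-up (LTF) after 3 years". The plan calls this allowance probably conservative, since "only 9% of D-CLIP participants have been lost to follow-up after a mean of 30 months".
- **Loss adjustment, primary endpoint (end of Aim 2).** To estimate a causal effect "adjusted for bias due to non-adherence and loss to follow-up, marginal structural models will be fit" around the analyses described before them. That includes the primary GEE. Their status relative to the intercept test is not stated, and covariates are not listed.
- **Loss adjustment, other endpoints (Aim 2).** For diabetes incidence, an adjustment for dependent censoring is planned if loss is not negligible, with a similar approach for regression to normoglycemia.
- **Intermediate data (Data Collection, Table 4).** The three risk factors are measured "at baseline and every twelve months after lifestyle classes begin". Medication use is also recorded annually, and class attendance is recorded.

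**The concern.** A GEE fitted to an indicator that does not exist for some participants drops them unless the plan says otherwise. The intercept then estimates success among those measured at 3 years, not among those enrolled. In a two-arm trial, similar dropout in both arms would partly cancel. Here there is no control arm, and the comparison is with a constant, so any difference in success between those lost and those retained goes straight into the estimate.

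The planned marginal structural models do not settle this. Adjusting for non-adherence moves the target towards the effect under adherence. A trial meant to inform scale-up needs the effect of offering the programme to everyone enrolled, corrected for loss alone. No such version is specified for the primary endpoint.

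If the lost did worse than those retained, the reported percentage is too high. When the true effect is small or nil, the trial could then be declared positive too often. If they did better, the error runs the other way. The documents do not say which to expect.

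**Working it through.** **Inputs from the documents.** Enrolled: 8 × 250 = 2000. Loss: 20% (planned maximum) and 9% (D-CLIP). Benchmark 21%, target 33%. Significance: "A probability of <0.05 will be considered statistically significant for all tests", taken here as two-sided.

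**Assumptions.** Success rate among the lost; equal site sizes; within-site correlation (ICC), since none is stated for the primary endpoint. The GEE is treated as a one-sample test of a proportion, with

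SE = √[p(1 − p)(1 + (m − 1) × ICC)/n].

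**1. The plan's power.** The trial "will have 93% or more power to detect an estimated difference" of 33% against 21%. At 20% loss, m = 200 and n = 1600. With no ICC given, the figure cannot be reproduced from stated inputs alone. Solving for the ICC that gives 93%:

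- normal test, variance at 33%: ICC 0.039. Check: SE = √(0.33 × 0.67 × 8.761/1600) = 0.0348; 0.12/0.0348 − 1.96 = 1.49; power 93%
- t with 7 df: 0.027
- null variance in the critical value: 0.047
- log scale: 0.064

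**2. Design effect, diluted by loss.** All-enrolled rate = (1 − L) × 0.33 + L × d, where L is the fraction lost and d is success among the lost.

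| L | d | All enrolled | Difference from 21% |
|---|---|---|---|
| 20% | 21% | 0.264 + 0.042 = 30.6% | 9.6 points |
| 20% | 10% | 0.264 + 0.020 = 28.4% | 7.4 points |
| 20% | 0% | 26.4% | 5.4 points |
| 9% | 0% | 0.91 × 0.33 = 30.0% | 9.0 points |

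Without dilution the difference is 12 points.

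**3. No true effect: all-enrolled rate exactly 21%.** Completer rate = (0.21 − L × d)/(1 − L).

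- L = 20%, d = 10%: 0.19/0.80 = 23.75%
- L = 9%, d = 10%: 0.201/0.91 = 22.1%
- L = 20%, d = 5%: 0.20/0.80 = 25.0%
- L = 9%, d = 5%: 0.2055/0.91 = 22.6%
- L = 20%, d = 0: 0.21/0.80 = 26.25%, the highest completer rate that loss alone can produce

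**4. Chance of declaring benefit in those cases.** The nominal figure in that tail is 2.5%. For L = 20%, d = 10%, ICC 0.01: SE = √(0.2375 × 0.7625 × 2.99/1600) = 0.0184; 0.0275/0.0184 = 1.49; Φ(1.49 − 1.96) = 32%. With ICC 0.039 the SE is 0.0315 and the ratio 0.87, which with a noncentral t on 7 df gives about 12%. The ranges below run from the t test at ICC 0.039 to the normal test at ICC 0.01. At 9% loss, m = 227.5 and n = 1820.

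| Success among the lost | 20% loss | 9% loss |
|---|---|---|
| 10% | 12–32% | 5–9% |
| 5% | 19–57% | 7–14% |

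The upper ends need ICC 0.01. Over the ICCs that reproduce 93% power (0.027–0.064), the 20%-loss figures are about 9–18% and 14–31%.

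**5. Counting all lost as failures.** Testing 26.4% of 2000 against 21%, with m = 250 and the null variance in the critical value, power is about 87% at ICC 0.01, 67% at 0.02 and 38% at 0.05.

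**The case against.** A reader might infer that the plan restricts the primary analysis to completers. It does not say so. That is the software default and it fits the 20% allowance, but the text is silent. A nearby secondary endpoint, cumulative diabetes incidence, codes everyone not meeting the definition as zero, which could keep the lost in the denominator. The defensible statement is that the rule is unspecified.

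A reader might also infer that the plan has no loss-only correction, or that the marginal structural models are merely supplementary. Neither is supported. A dependent-censoring adjustment without non-adherence is planned for diabetes incidence, with a similar approach for regression to normoglycemia. The marginal structural models cover the primary endpoint and are given no rank. They belong to the same family as censoring weights, so part of the remedy is already in the plan.

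On size, 20% is the planned ceiling, and at the 9% seen in D-CLIP the distortion is much smaller. The direction of bias and the success rates among the lost are assumptions. The plan also argues that 21% is a demanding benchmark, because D-CLIP controls received a minimal intervention. If that 21% itself omits the D-CLIP losses, part of the bias cancels.

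All of this stands and limits the claim. It does not supply a missing-outcome rule or a loss-only estimate for the primary endpoint.

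**Conclusion.** The point holds in limited form. The primary GEE has no stated analysis set or missing-outcome rule, and run as written it defaults to those measured at 3 years. The only loss adjustment that reaches it is joint with non-adherence and so answers a different question.

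The consequence depends on the observed rate. A completer rate up to about 26% at 20% loss, or about 23% at 9% loss (0.21/0.91), could be wholly due to dropout. At the design effect, loss shrinks the result but cannot remove it: even if every lost participant fails, 26.4% exceeds 21%. The stronger reading, that dropout could account for a 33% completer result at the plan's own loss rate, is therefore wrong.

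The inflated error rates rest on the assumed success among the lost (5–10%), the assumed ICC, and a benchmark that does not share the same omission. The gap in specification rests on none of these.

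**What to change.** Define the primary analysis on all enrolled participants and state the rule for missing 3-year outcomes. Two suitable methods are:

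- inverse-probability-of-censoring weights for loss only; or
- multiple imputation of 36-month systolic blood pressure, triglycerides and HbA1c, from which the indicator is then derived.

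Either should use baseline, 12- and 24-month values, attendance, medication and site. Then fit the planned GEE.

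Report completers as a sensitivity analysis. Keep the adherence-adjusted marginal structural model separate, with its target and status stated. Add sensitivity analyses with the lost set to 21% and to failure. Note that missing-as-failure is conservative if the D-CLIP 21% is itself completer-based, and that its power may be low (step 5 of the working).

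**Cost.** SAP wording and a little more analysis on data already scheduled for collection. The price is a missing-at-random assumption and probably a smaller estimate.
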